#### **7.1.4. Early Withdrawal from Treatment and Safety Follow-up Period**

Subjects who prematurely discontinue the main study should be strongly encouraged to complete the final efficacy evaluations scheduled for Week 208/EOT as applicable, and the safety follow-up evaluations scheduled for the Week 210/EOS visit (4 weeks following the last dose).

Subjects who withdraw prior to week 104 will not be eligible to participate in the OLE.

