- l.) Pamrevlumab infusion is NOT to be administered at week 208 (EOT)
- m.) AEs and SAEs are collected from date of consent through EOS.
- n.) Concomitant medications and nondrug therapies must be reported beginning after informed consent is obtained and ends 30 days after the last treatment.
- o.) Specialty labs for HAHA (human anti-human antibody) / Neutralizing Antibody
- p.) Subjects who terminate prior to Week 208/EOT should complete the Early Termination (ET) visit.
- q.) Assessment required only if subject terminated study prior to Week 208
- r.) 208 weeks is an estimation of maximum duration for OLE. Actual duration of the OLE will be determined at the Sponsor's program level.

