3. STUDY OBJECTIVES

3.1. Primary Objective

The primary objective of this trial is to evaluate long-term efficacy and safety of pamrevlumab in non-ambulatory DMD subjects who have been previously treated with pamrevlumab for a minimum of 104 weeks.

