9.2.3. Change from Baseline in Efficacy Endpoints with MMRM

The following efficacy endpoints will be analyzed with MMRM method.

1. At Week 48, Week 96, Week 144, and Week 192
 - a. Change from baseline in PUL total score, including middle and distal score
 - b. Change from baseline in grip strength. The grip strength should be reported by dominant and non-dominant hand separately.
2. At Week 52, Week 104, Week 156, and Week 208
 - a. Change from baseline in LVEF%
 - b. Change from baseline in cardiac MRIs including cardiac fibrosis score assessed by Late Gadolinium Enhancement (LGE)
 - c. Change from baseline in Myocardial Circumferential Strain [Global Circumferential Strain (GCS)]

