9.2.4. Exploratory Analysis - Comparison with the CINRG natural history data

Efficacy endpoints: % predicted FCV (ppFVC), LVEF, and grip strength in dominant hand will be compared with a subset of CINRG DMD Natural History study (DNHS) data with all 36 subjects using a random coefficient model (RCM). The other outcome measures including Performance of Upper Limb (PUL), cardiac fibrosis by LGE, and Myocardial Circumferential Strain [Mean Peak Circumferential strain (MPCS) and Global Circumferential Strain (GCS) percentage] assessed by cardiac MRI are not available in CINRG data and therefore will not be compared.. The RCM model will use efficacy data from both the main and OLE periods and include continuous variable avisityr (calculated as the elapsed days of assessment date from main study baseline date in the unit of year), treatment trt (079 subjects as treated with trt = 1, and subjects in CINRG data as control with trt =0), the interaction term of trt and avisityr, and baseline endpoint as fixed effects, while the intercept and avisityr are included as random effects. The strategy for covariance structure for the within-patient errors in the model is the same as what is described in [Section 9.2.2.1](#). The LSMean (SE) for annual change (slope) as well as LSMean (SE) and 95% CI of treatment differences between pamrevlumab and control of estimated changes from baseline at year 1, year 2, year 3 and year 4 in the OLE period will be presented. The sample SAS code is provided in [Appendix 2](#).

Line plots of each subject's efficacy trajectory compared with the mean plot of the CINRG will be provided.

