APPENDIX 2. SAMPLE SAS CODE FOR RCM ANALYSIS

SAS code for this model, using the primary endpoint ppFVC as example, is provided below.

```

/*Random Coefficient Model (RCM) to estimate the change at year 1, 2, 3 and
4*/
/*avisityr is the actual number of years from Day 1, avisityr=4 will be
the change from baseline at year 4 */
/* fvc0= baseline ppFVC, should be used for change in FVC */
/* &meanfvc0= the mean of the baseline ppFVC           */

proc mixed data = fvc_obs;
  class subjid;
  model chgfvc = avisityr fvc0/solution cl covb outp=pred_fvc cl;
  random intercept avisityr /subject=subjid type=CS;
  ESTIMATE 'Change from Baseline at Year 1' intercept 1 avisityr 1 fvc0
  &meanfvc0 / CL;
  ESTIMATE 'Change from Baseline at Year 2' intercept 1 avisityr 2 fvc0
  &meanfvc0 / CL;
  ESTIMATE 'Change from Baseline at Year 3' intercept 1 avisityr 3 fvc0
  &meanfvc0 / CL;
  ESTIMATE 'Change from Baseline at Year 4' intercept 1 avisityr 4 fvc0
  &meanfvc0 / CL;
  ods output SolutionF=mxparms CovB=mxcovb Estimates=chgfrbl;
run;

```

Sample SAS code for comparison 079 OLE data (trt = 1) with CINRG (trt = 0).

```

PROC MIXED DATA = final;
  CLASS trt SUBJID ;
  MODEL chg = trt|avisityr base/ SOLUTION DDFM=KR;
  RANDOM intercept avisityr / SUBJECT =SUBJID TYPE=UN GROUP= trt;

  LSMEANS trt/ at avisityr = 1 PDIFF CL;
  LSMEANS trt/ at avisityr = 2 PDIFF CL;
  LSMEANS trt/ at avisityr = 3 PDIFF CL;
  LSMEANS trt/ at avisityr = 4 PDIFF CL;

  ods output LSMeans=LSMeans_chg diffss=diffs_chg;
RUN;

```

Statistical Analysis Plan

Addendum

TITLE PAGE

PROTOCOL TITLE: A Trial of FG-3019, a Monoclonal Antibody to Connective Tissue Growth Factor, in Non-Ambulatory Subjects with Duchenne Muscular Dystrophy (DMD)

PROTOCOL NUMBER: Protocol FGCL-3019-079

STUDY SPONSOR: FibroGen, Inc.
[name]
[name]

STUDY DRUG: Pamrevlumab

INDICATION: Duchenne Muscular Dystrophy (DMD)

SAP VERSION Addendum v1.1

RELEASE DATE August 08, 2023

[figure not shown]
CONFIDENTIALITY STATEMENT

The information contained in this document is confidential and proprietary to FibroGen, Inc. No part of this document or any of the information contained herein may be transmitted, disclosed, shared, reproduced, published or utilized by any persons without prior written authorization by FibroGen, Inc.

SIGNATURES AND APPROVALS**Approvals**

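### The pamrevlumab–CINRG contrasts at years 1 to 4 are timed from the main-study baseline but are to be reported as OLE years

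*SAP*

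**What the plan says.** **CINRG comparison (SAP 9.2.4, Appendix 2).** The model uses efficacy data from both the main study and the OLE. Its time variable, avisityr, is "calculated as the elapsed days of assessment date from main study baseline date in the unit of year". The sample code evaluates the treatment difference at avisityr 1, 2, 3 and 4, the last statement being "LSMEANS trt/ at avisityr = 4 PDIFF CL", with no offset for time already spent in the main study. The results are then described as follows: "estimated changes from baseline at year 1, year 2, year 3 and year 4 in the OLE period will be presented". The heading above the code also calls the study data OLE data, although 9.2.4 says both periods are used.

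**Entry to the OLE.** Protocol 7.1.4: "Subjects who withdraw prior to week 104 will not be eligible to participate in the OLE". SAP 3.1 describes the subjects as "previously treated with pamrevlumab for a minimum of 104 weeks". Protocol Appendix 4 schedules main-study treatment visits up to Week 208/EOT. On the length of the OLE, footnote r of the schedule in Protocol Appendix 6 says "208 weeks is an estimation of maximum duration for OLE".

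**MMRM (SAP 9.2, 9.2.3, 13).** PUL and grip strength are analysed as follows: "At Week 48, Week 96, Week 144, and Week 192". LVEF and the cardiac MRI measures follow their own schedule: "At Week 52, Week 104, Week 156, and Week 208". SAP 13 places these visits in the OLE. Both 9.2 (as the default) and 13 (for this MMRM) take change from the main-study baseline. The model terms in 9.2.3.1 are visit, baseline and age.

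**Single-arm RCM (SAP 9.2.2.1, Appendix 2).** The text counts time from a baseline date without saying which one, and labels the estimates as OLE years. The code comment counts from Day 1.

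**The concern.** The time variable and the label in 9.2.4 cannot both be right. A reader of the study report who sees a difference for OLE year 1 will take it as the first year of the extension. On the stated clock it is the first year of the main study. The contrasts are the SAP's only specified year-by-year estimates against an external control, and the stated objective of this SAP is long-term efficacy after at least 104 weeks of treatment, so the label bears directly on what the table appears to show.

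The MMRM raises a related question of clocks. Its change score starts at the main-study baseline and its visits are counted from OLE entry. Subjects who spent different lengths of time in the main study then share one visit mean, although they have been on treatment for different times since the baseline used.

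**Working it through.** **1. Inputs.** Time origin: main-study baseline (SAP 9.2.4). Evaluation points: 1, 2, 3, 4 (Appendix 2). Earliest OLE entry: Week 104 (Protocol 7.1.4). Last scheduled main-study treatment visit: Week 208 (Protocol Appendix 4). Actual entry times are not given, so Weeks 104, 156 and 208 are used to show the range. Assumptions: a year is 365.25 days, the baseline date is the first dose, and visits are exactly on schedule.

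**2. Model years expressed in OLE weeks.** Formula: OLE week = k × 365.25/7 − entry week. A negative value is before OLE entry.

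| Model year k | Main-study week | Entry Week 104 | Entry Week 156 | Entry Week 208 |
|---|---|---|---|---|
| 1 | 52.2 | −51.8 | −103.8 | −155.8 |
| 2 | 104.4 | 0.4 | −51.6 | −103.6 |
| 3 | 156.5 | 52.5 | 0.5 | −51.5 |
| 4 | 208.7 | 104.7 | 52.7 | 0.7 |

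No entry time makes all four years OLE time. Year 2 is 730.5 days against 728 days for Week 104, so it falls 2.5 days after the earliest possible entry.

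**3. How firm is the year 2 figure?** Protocol 7.1.1 uses both a screening test (from Day −28) and a repeat (Day 0 up to Week 2) to establish baseline for pulmonary and muscle function. SAP 5.4.3 refers the main-study baseline to the main-study SAP, whose definition is not in the documents. With a baseline date of Day 14, year 2 is 14 + 730.5 − 728 = 16.5 days after Week 104. With Day −28 it is −28 + 730.5 − 728 = −25.5 days, before entry. Visits are also scheduled from the previous visit with a ±2 day window, and OLE Day 0 may follow the main-study EOT visit by up to 7 days. Year 2 therefore moves by some weeks either way. The year 1 conclusion does not change.

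**4. Part of the OLE beyond the last contrast.** If the OLE ran 208 weeks, 208 − 104.7 = 103.3 weeks (entry Week 104) to 208 − 0.7 = 207.3 weeks (entry Week 208) would follow year 4. Those data still enter the slope and the line plots.

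**5. What the label does to a reading (illustration).** Assume a constant difference of 3 points of percent predicted FVC per year, the gap between the protocol's −2% and −5%. The contrast at year 1 is 3 points. The cumulative difference since main-study baseline at the end of the first OLE year would be about 3 × 3 = 9 points (entry Week 104) to 3 × 5 = 15 points (entry Week 208).

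**6. MMRM clock.** The windows in SAP Appendix 1 reproduce: for cardiac MRI, (7 × 156 + 1) + 182 − 1 = 1274, so the last window opens at Day 1275, as stated. Muscle function tests are 12-weekly in the OLE (Protocol Appendix 6), which gives Weeks 48, 96, 144 and 192. The main-study tables, as extracted, show these tests at 60, 72, 84, 104, 116, 128, 140 and 156, with none at 96 or 144. With SAP 13, this identifies the visits as OLE weeks.

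Change from the main-study baseline at OLE week w then covers L + w weeks, where L is main-study duration. The smallest total at Week 48 is 104 + 48 = 152 weeks. As an illustration only, assuming linear decline (which SAP 9.1 says the MMRM does not assume):

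- Main-study share L/(L + w) at Week 48: 104/152 = 0.68 to 208/256 = 0.81. At Week 192: 104/296 = 0.35 to 208/400 = 0.52.
- A subject entering 52 weeks later than a Week 104 entrant: 204/152 = 1.34 times the change at Week 48, and 348/296 = 1.18 times at Week 192.

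The ratios approach 1 if entry times were similar.

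**7. Single-arm RCM.** SAP 9.2 gives the main-study baseline as default. SAP 9.2.2.1 does not name the baseline. The code comment says Day 1, which is the first dose in 5.5 and the first OLE dose in 13. This is a difference of wording; no passage clearly specifies a mismatched model.

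**The case against.** The strongest reply is that this is a label and nothing more. The clock is stated in the same paragraph, the code follows it, the slope does not depend on it, and the analysis is exploratory. All of that stands. It limits the severity, but it does not make the label true.

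Three stronger readings are tempting and are not supported.

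- *The CINRG model is misspecified.* SAP 9.2 makes the main-study baseline the default for the change score, and 9.2.4 uses the same origin for time. The model is consistent on its own clock.
- *The MMRM baseline contradicts itself across sections.* SAP 9.2 and 13 both name the main-study baseline. SAP 5.4.3 defines both baselines and assigns neither to the MMRM, and the baseline rows in Appendix 1 are visit windows. What survives is the combination of that baseline with OLE-week visits, with no model term for main-study duration.
- *The single-arm RCM is wrong.* It can be read consistently as an OLE analysis counted from the first OLE dose. Only the wording needs settling.

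It is also fair to say that cumulative change since first treatment is a legitimate quantity for a long-term objective. The shares in step 6 restate what that quantity contains; they do not measure an error.

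**Conclusion.** The point holds as a labelling error in SAP 9.2.4, of minor to moderate severity. Year 1 is main-study time for every subject. Year 2 is at most roughly the start of the OLE: 2.5 days after the earliest entry if baseline is the first dose and visits are on schedule, and shifted by some weeks otherwise. Years 3 and 4 are main-study or OLE time depending on entry. The annual slope and the Week 104 primary endpoint are unaffected, and no OLE success criterion depends on these contrasts.

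The secondary point also holds: each MMRM visit mean includes at least two years of main-study change and pools subjects with different main-study durations. Its size cannot be known without the entry times, and the figures in step 6 rest on assumed entry times and linear decline.

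**What to change.** 1. **SAP 9.2.4:** keep the change score, baseline covariate and avisityr on the main-study origin, and replace *in the OLE period* with *since main-study baseline*. Correct the heading above the CINRG code in Appendix 2 to main plus OLE data.
2. **MMRM:** choose one clock and make 9.2, 9.2.3, 13 and Appendix 1 agree. One option is change from the OLE baseline (5.4.3) at OLE weeks. The other keeps the main-study baseline and indexes visits to the first main-study dose. The second needs visit weeks that match the main-study schedule and extended windows: the last cardiac MRI window is open from Day 1275, so on a main-study clock it would pool everything from Week 182 onward ((1275 − 1)/7 = 182).
3. **SAP 9.2.2.1:** name the baseline and time origin, and align the code comment and year labels.
4. **Report** the distribution of main-study duration at OLE entry.

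The cost is SAP wording, a code heading and a code comment, plus a re-indexed MMRM run and possibly longer windows. No new data are needed.

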10. SAFETY ANALYSIS

10.1. Adverse Events

All reported AEs will be presented in listings. For the OLE period of the 3019-079 study, the treatment emergent period of safety reporting for the Clinical Study Report (CSR) is defined as from the first infusion date to the last infusion date + min (60 days, EOS date -last infusion date+1) for those subjects in the open label extension (OLE) period.

Number (%) of subjects with a treatment emergent adverse events (TEAEs) in the treatment emergent period of safety reporting (OLE period) will be summarized by system organ class (SOC) and preferred term (PT). The summary tables will be sorted alphabetically by SOC and by decreasing order of frequency of PT within each SOC. A subject with multiple adverse events within a SOC is only counted once in this SOC. Similarly, a subject with multiple adverse events within a PT is only counted once in this PT.

The exposure adjusted incidence rate, number of subjects with the event/total patient exposure years (PEY)*100, will be summarized, system organ class (SOC) and preferred term (PT).

The patient exposure years (PEY), (last infusion date – first infusion date + 1)/365.25, for each subject will be summed to calculate the total patient exposure years. The summary tables will be sorted alphabetically by SOC and by decreasing order of frequency of PT within each SOC. A subject with multiple adverse events within a SOC is only counted once in this SOC. Similarly, a subject with multiple adverse events within a PT is only counted once in this PT. In addition to listing of all reported AEs and summary of all TEAEs, the following TEAE summaries will be provided:

- TEAEs
- TEAEs (grade 3 and higher per CTCAE)
- TEAE leading to treatment discontinuation
- TEAE and relationship to FG-3019 (pamrevlumab)
- TEAE and severity
- TESAE and relationship to FG-3019 (pamrevlumab)
- Most frequent (non-serious) TEAEs ($\geq 5\%$)
- Listing of Deaths
- Listing of Serious Adverse Events
- Listing of TEAE leading to treatment discontinuation

In addition, special safety events such as hypersensitivity, anaphylactic and infusion reactions will be included.

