2. STUDY DESIGN

This study is designed as the open-label extension (OLE) of the main study FGCL-3019-079. All subjects participating in the OLE must have completed treatment through the primary endpoint and completed the End of Treatment (EOT) visit of the main study FGCL-3019-079.

Each subject in the OLE receives pamrevlumab (35 mg/kg, every 2 weeks) for up to 208 weeks. The dosing period began on the first day of dosing with study treatment (Day 1) in the OLE, which is to be conducted simultaneously with, or within 7 days after the parent study EOT visit. The dosing period continued until Week 208/EOT.

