13. CHANGES FROM PROTOCOL

- The date of the first dose in the OLE period will be considered as the date of Day 1 for all analyses during the OLE period, instead of Day 0.
- Efficacy parameters, including change from baseline of the main study in ppFVC, PUL, grip strength, LVEF%, and cardiac MRIs including cardiac fibrosis score assessed by Late Gadolinium Enhancement (LGE), and Myocardial Circumferential Strain [Global Circumferential Strain (GCS)], will be analyzed at Week 48/52, Week 96/104, etc. in the OLE period using Mixed Model for Repeated Measures (MMRM) additionally.

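### The exposure-adjusted adverse event rate keeps adding person-time after a subject's first event, so it is capped at 100/mean exposure and understates the most frequent events

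*SAP*

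**What the plan says.** SAP 10.1 (Adverse Events) gives the rate as "number of subjects with the event/total patient exposure years (PEY)*100", by system organ class (SOC) and preferred term (PT). The denominator is built from each subject's whole dosing span: "last infusion date – first infusion date + 1)/365.25, for each subject will be summed to calculate the total patient exposure years". On the numerator side, "a subject with multiple adverse events within a PT is only counted once in this PT", and the same rule applies within a SOC. Nothing in the section ends person-time at first onset, and no rate based on event counts is planned.

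The window for counting events is longer than the window for exposure. It ends at "last infusion date + min (60 days, EOS date -last infusion date+1"), whereas PEY stops at the last infusion.

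Three other places fix the time scale. SAP 13 sets the clock: "The date of the first dose in the OLE period will be considered as the date of Day 1 for all analyses during the OLE". SAP 2 gives the planned duration: "Each subject in the OLE receives pamrevlumab (35 mg/kg, every 2 weeks) for up to 208 weeks". The footnotes to the OLE schedule in Protocol Appendix 6 qualify it: "208 weeks is an estimation of maximum duration for OLE", with actual duration decided at program level. The same footnotes rule out an infusion at Week 208, so the last scheduled infusion is at Week 206.

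SAP 10.1 also plans the number and percentage of subjects by SOC and PT, and listings of all adverse events.

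**The concern.** An incidence rate for first events needs a denominator made up of time during which a first event could still occur. Here, once a subject has had the event, that subject adds nothing more to the numerator but keeps adding to the denominator until the last infusion. For an event that most subjects eventually have, the reported figure says more about how long subjects were dosed than about how fast the event occurs. With a constant true hazard it falls as follow-up lengthens.

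Long-term safety is part of the OLE's primary objective (SAP 3.1), and long follow-up is where this formula departs furthest from a rate. Anyone who sets the OLE figure beside one from a shorter pamrevlumab period, computed the same way, would see an apparent fall with no change in the underlying hazard.

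**Working it through.** The documents state no numerical adverse event rate, so there is no figure of the plan's own to reproduce.

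**Inputs from the documents.** Subjects are counted once per term, and PEY is first to last infusion (SAP 10.1). The last scheduled OLE infusion is at Week 206 (Protocol Appendix 6). Events count for up to 60 days after the last infusion (SAP 10.1).

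**Assumed.** Mean OLE exposure and event hazards are not given. I take exposures from 1 to 3.95 years, the same for all subjects, and a constant hazard to first event.

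**Step 1: the ceiling.** If all N subjects have the event, the rate is 100 × N / (N × mean PEY) = 100/mean PEY. This is algebra and needs no hazard assumption.

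| Dosed to | PEY = (7 × weeks + 1)/365.25 | Ceiling per 100 patient-years |
|---|---|---|
| Week 52 | 365/365.25 = 0.999 | 100.1 |
| Week 104 | 729/365.25 = 1.996 | 50.1 |
| Week 156 | 1093/365.25 = 2.992 | 33.4 |
| Week 206 | 1443/365.25 = 3.951 | 25.3 |

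**Step 2: understatement by crude incidence.** Let p be the proportion with the event over exposure T. The SAP figure is 100p/T. The first-event rate is 100L, with L = −ln(1 − p)/T. Their ratio is p/(−ln(1 − p)). At T = 3.95 years:

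| Crude incidence p | SAP figure | First-event rate | Ratio | Understated by |
|---|---|---|---|---|
| 5% | 1.3 | 1.3 | 0.975 | 2.5% |
| 10% | 2.5 | 2.7 | 0.949 | 5% |
| 20% | 5.1 | 5.6 | 0.896 | 10% |
| 50% | 12.7 | 17.5 | 0.721 | 28% |
| 80% | 20.2 | 40.7 | 0.497 | 50% |
| 90% | 22.8 | 58.3 | 0.391 | 61% |

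T cancels from the ratio, so for a given p the percentage is the same at any common exposure. Exposure matters because longer dosing raises p for a given hazard. A SOC row pools its PTs, so its p is at least that of any one of them.

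**Step 3: dependence on follow-up.** For a fixed hazard the SAP figure is 100(1 − exp(−L × T))/T. With L = 0.50 per year (50 per 100 patient-years), it is 31.6 at 104 weeks and 21.8 at 3.95 years. That is a fall of (31.6 − 21.8)/31.6 = 31% with no change in hazard.

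**Step 4: the tail after the last infusion.** Sixty days is 60/365.25 = 0.164 years, which is 4.2% of 3.95 years and 16.4% of 0.999 years. Counting events over T + 0.164 but dividing by T raises the figure:

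- T = 3.95 years, true rate 10 per 100 patient-years: the ratio to the true rate moves from 0.826 to 0.854, a partial offset.
- T = 1 year, true rate 5 per 100 patient-years: the ratio moves from 0.975 to 1.131, a reversal.

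These use the full 60 days. The tail is shorter when the end-of-study date comes first.

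**The case against.** The best defence is that this is a secondary descriptive figure with its formula stated, reported next to outputs that do not share the defect. SAP 10.1 gives numbers and percentages by SOC and PT, and SAP 8.1 tabulates exposure. A term affecting 90% of subjects will be shown as 90%. No test, decision or stopping rule uses the rate. All of this stands, and it limits the consequence. It does not repair the rate, because the crude percentage makes no adjustment for exposure, which is the only reason to report the rate.

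Three stronger readings are tempting, and the documents do not support them.

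- *A reader might infer that the rate has a fixed ceiling near 25 per 100 patient-years.* That needs essentially every subject dosed to Week 206. The plan gives only an estimated maximum, Protocol Appendix 6 allows the OLE to end earlier, and the exposure categories in SAP 8.1 start at 26 weeks or less. About 25 is the lowest ceiling under the planned schedule. At shorter mean exposure it is higher.
- *A reader might infer that common adverse events in general are strongly understated.* SAP 10.1 sets its most-frequent threshold at 5% of subjects, where the bias is 2.5%. It is 5% at 10% incidence and becomes large only when about half or more of subjects are affected.
- *A reader might infer that the plan will present a misleading fall in rates from the main period to the OLE.* No such comparison is planned. Protocol Appendix 6 says only that extension data are summarised descriptively along with the main study. The original main-study SAP is not among the documents, and the external comparison in SAP 9.2.4 covers efficacy endpoints only.

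**Conclusion.** The formula is wrong for the label it carries. It does not estimate an incidence rate when a large share of subjects have the event, and no other section corrects it. The ceiling of 100/mean PEY holds without assumptions, although its value is unknown because mean exposure is not given. The understatement is negligible to small for events affecting 5 to 10% of subjects, 28% at 50% and 61% at 90%. These percentages rest on a constant hazard and equal exposure.

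The mismatch between the counting window and PEY is a second, smaller inconsistency. It partly offsets the bias, and it can reverse it for rare events with short exposure.

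The harm lies in reading this figure as an incidence rate, or comparing it across periods of different length, and mainly in the most frequent PT and SOC rows. The planned crude percentages mean that no common event is concealed. The efficacy analyses are untouched.

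**What to change.** In SAP 10.1, define time at risk separately for each SOC and PT:

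- subjects with the event: first OLE infusion to first onset of that SOC or PT;
- all other subjects: first OLE infusion to the end of the treatment-emergent period.

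The rate is then 100 × subjects with the event / total time at risk. This removes the ceiling and brings numerator and denominator onto the same window. Optionally, add an event-count rate: all events per 100 patient-years over total treatment-emergent time.

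The change uses onset, infusion and end-of-study dates that the analysis already needs. Partial onset dates would follow the existing imputation rules in SAP 5.4.1. The cost is SAP wording and minor programming, with no change to design or data collection. Reported rates for frequent events will be higher: under the assumptions above, an event in half of the subjects over 3.95 years moves from 12.7 to 17.5 per 100 patient-years, before alignment of the post-infusion window.

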### 3. Study Visits

All study visits will be performed in accordance with the Schedule of Assessments presented in [Section 6](#).

The dosing period begins on the first day of dosing with study treatment (Day 0), which is to be conducted simultaneously with, or within 7 days after the parent study EOT visit. The dosing period continues until the last subject from the phase 3 DMD program completes 52 weeks of treatment on OLE or when pamrevlumab is commercially available or when the Sponsor decides to end the study. Subjects will receive study drug every 2 weeks. The visit window for these visits is  $\pm 3$  days. Each visit should be scheduled based on the previous visit, not the Day 0 (baseline) visit.

Muscle or pulmonary function tests that cannot be performed or produce inadequate results according to test procedures during a specified visit should be performed by the next scheduled dosing visit.

Cardiac MRI may be performed within  $\pm 2$  weeks of the specified visit.

Subjects who complete the dosing period must have their end of treatment assessments performed at the Week 208/EOT visit. The end of treatment Cardiac MRI may be performed any time from Week 208/EOT to Week 210/EOS/ET (End of Study / Early Termination) visit.

Subjects who prematurely discontinue the study will be strongly encouraged to complete the final efficacy evaluations scheduled for Week 208/EOT as applicable, and the safety follow-up evaluations scheduled for the Week 210/EOS/ET visit (4 weeks following the last dose) and a final safety follow-up phone call 60 days (+3 days) after the last dose of pamrevlumab as per the schedule of assessments..

For all subjects, the final safety assessments should be completed at the Week 210/EOS/ET visit, 4 weeks ( $\pm 7$  days) after the last dose of pamrevlumab and a final safety follow-up phone call 60 days (+3 days) after the last dose of pamrevlumab as per the schedule of assessments.

In the event that any visit is missed, assessments should be performed as soon after the missed visit as feasible. Missed infusions will not be replaced.

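### The exposure-adjusted adverse event rate in SAP 10.1 counts events after the last infusion but no person-time after it, so numerator and denominator cover different periods

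*SAP*

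**What the plan says.** All the definitions that matter are in SAP section 10.1, Adverse Events.

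- **Numerator period.** The treatment-emergent period runs "from the first infusion date to the last infusion date + min (60 days, EOS date -last infusion date+1" days. It therefore closes 60 days after the last infusion or one day after the EOS date, whichever comes first.
- **Rate.** It is "number of subjects with the event/total patient exposure years (PEY)*100", by system organ class and preferred term. Each subject counts once per term.
- **Denominator.** "The patient exposure years (PEY), (last infusion date – first infusion date + 1)/365.25, for each subject will be summed". Nothing is added after the last infusion.

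Both periods start at the first OLE dose. SAP section 13 states: "The date of the first dose in the OLE period will be considered as the date of Day 1 for all analyses".

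The tail is real follow-up. Protocol Appendix 6, section 3 (Study Visits) says the final safety assessments "should be completed at the Week 210/EOS/ET visit, 4 weeks" after the last dose, with a 7-day window either way, and adds a safety call at 60 to 63 days. The OLE schedule (Appendix 6, section 6) marks adverse event collection at both contacts, although its footnote m ends collection at EOS. The SAP text does not say which contact supplies the EOS date.

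Footnote r to the same schedule leaves the length of the extension open: "Actual duration of the OLE will be determined at the Sponsor's program level".

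**The concern.** An event in the tail enters the numerator, while the days in which it could occur are missing from the denominator. The shorter a subject's exposure, the larger the tail is relative to the counted time, so a rate meant to adjust for length of exposure shifts with that length.

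This is the only length-adjusted safety summary in the SAP, and the sponsor sets the length of the extension. Protocol Appendix 6, section 5 says the extension data will be summarised along with the main study. A reader may set these rates beside main-study rates, or beside rates from another study, and take them as comparable.

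The same formula has a second feature. A subject counts once, but person-time continues after that subject's first event. This lowers the rate, so the two features must be looked at together before any direction is claimed.

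**Working it through.** The documents give no adverse event rate and no total person-time, so there is no planned figure to reproduce. The size follows from the two definitions.

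**Inputs**

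- D = last infusion − first infusion + 1, in days (SAP 10.1). There is no infusion at Week 208 (OLE schedule footnote l), so the last scheduled one is at Week 206 and D = 206 × 7 + 1 = 1443 days, or 3.95 years. Likewise D = 729 at Week 104, 365 at Week 52 and 183 at Week 26.
- T = min(60, EOS − last infusion + 1), in days. If EOS is the Week 210/EOS/ET visit at 28 ± 7 days, T = 29 (range 22 to 36). If EOS is the final call at 60 to 63 days, T = 60, the cap.
- The stopping patterns below are assumptions; the documents give none.

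**Step 1: effect of the mismatch alone.** The SAP sums person-time over subjects, so the SAP rate divided by the window-matched rate is Σ(D + T)/ΣD. The excess is ΣT/ΣD.

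| Assumed exposure | T = 29 | T = 60 |
|---|---|---|
| All dosed to Week 206 | 29/1443 = 2.0% | 60/1443 = 4.2% |
| Half stop at Week 52, half at Week 206 (10 + 10 subjects; D sums to 3650 + 14430 = 18080) | 580/18080 = 3.2% | 1200/18080 = 6.6% |
| Half stop at Week 26, half at Week 206 (mean D = 813) | 29/813 = 3.6% | 60/813 = 7.4% |
| Mean exposure one year (365.25 days) | 7.9% | 16.4% |

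**Step 2: direction against the true incidence rate.** Assume a constant hazard λ per year, with D and T in years. The expected SAP rate is [1 − exp(−λ(D + T))]/D. Matching the windows but letting person-time run past the first event gives [1 − exp(−λ(D + T))]/(D + T). Results per 100 patient-years, with T = 60 days:

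| True rate | Last infusion | SAP formula | Windows matched only |
|---|---|---|---|
| 2 | Week 206 | 2.00 | 1.92 |
| 10 | Week 206 | 8.54 | 8.20 |
| 2 | Week 26 | 2.64 | 1.99 |
| 10 | Week 26 | 12.85 | 9.67 |

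With dosing to Week 206, the two effects cancel at a true rate of about 2.0 per 100 patient-years (60-day tail) or 1.0 (29-day tail). Above that the SAP formula understates. With a 60-day tail the crossover is about 7.4 at Week 104 and about 27 at Week 52.

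**Step 3: dependence on length.** At a true 10 per 100 patient-years, the SAP formula gives 12.85 for 26 weeks of dosing and 8.54 for 206 weeks, a ratio of about 1.5. Matching the windows reduces it to 9.67/8.20 = 1.18. The rest comes from person-time after the first event.

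**Step 4: person-time to first event within the TEAE window.** With window W = D + T, expected person-time per subject is [1 − exp(−λW)]/λ and expected events are 1 − exp(−λW). Their ratio is λ for any W, so the dependence on length disappears under this model.

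**The case against.** The strongest reply is that the SAP defines a rate per exposure year, states the formula in full and uses the first-to-last-infusion interval of its exposure summary in section 8.1. A reader can convert it. The rate is descriptive, the extension has one arm, and Protocol section 9.4.7 applies no inferential procedures to safety data. Subject counts, percentages and listings are untouched, and the only external comparison in the SAP (section 9.2.4) concerns efficacy. All of this limits the consequence. It does not remove the mismatch: if the denominator is to mean time on drug, the numerator should stop there too, and no passage makes it do so.

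Two stronger readings are tempting, and the documents do not support them.

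- A reader might infer that the rate is simply overstated. That holds only against a window-matched denominator. Step 2 shows that for common events over long exposure the SAP formula falls below the true rate, and that matching the windows alone moves it further away (8.54 to 8.20 against a true 10).
- A reader might take single-subject ratios such as 60/365 = 16.4% or 60/183 = 32.8% as the error in the reported rate. The SAP pools person-time, so early stoppers act only through their share. A pooled 32.8% would need mean exposure of about 26 weeks, which nothing in the documents indicates. Footnote r shows that duration may vary, not that it will be short. Sixty days is also a cap; if EOS is the Week 210 visit, the usual tail is 29 days.

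**Conclusion.** The inconsistency is certain from the text of SAP 10.1: the numerator window extends past the last infusion, the denominator does not, and nothing elsewhere aligns them. Its size is modest. Relative to a window-matched denominator, the pooled rate is too high by about 2% to 4% with full dosing, 3.2% to 6.6% if half the subjects stop at Week 52, and about 8% to 16% if mean exposure is one year. The lower figure in each range assumes a 29-day tail and the upper one the 60-day cap.

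Whether the reported rate lies above or below the true incidence rate depends on event frequency and exposure length, because person-time is also not stopped at the first event; that part of the working rests on an assumed constant hazard. No hypothesis test or between-arm comparison is affected. What is lost is comparability: the rate is not like for like across periods or studies of different length.

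**What to change.** In SAP section 10.1:

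1. For each system organ class and preferred term, define a subject's person-time as (earlier of first event onset and end of that subject's treatment-emergent period − first OLE infusion date + 1)/365.25, using the same end date that defines a TEAE.
2. State which contact supplies the EOS date: the Week 210/EOS/ET visit or the final safety call.
3. Keep first-to-last-infusion time for the exposure summary in section 8.1 only.

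Item 1 deals with both features together; changing only the end date would leave the downward one in place. The cost is one line of SAP text and one derived variable per term, with no new data collection.
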